**The outcome for Aim 1 is rate of high-risk categorization.**

The analysis for this aim does not compare the outcome between arms as our aim is to determine if using MeTree to collect FHH improves the rate of high-risk identification for CRC compared to what is currently available administratively in VA. In our study design, both arms use MeTree to collect FHH, so the design for the aim is a pre-/post- comparison within Veterans. A binary variable will be created for each participant (1=presence of high-risk for CRC, 0=absence) at baseline (current practice) and following MeTree administration. We will test whether the rate of high-risk identification is higher following the MeTree administration compared to what is available in the medical record under current practice using a McNemar's test adjusted for PCP clustering. In addition to examining identification rates, specification of the source of identification of high-risk CRC will be important to formulating a standard identification strategy for clinical follow-up (e.g., referral to or receipt of colonoscopy screening).

**Table 2. Estimated differences in CRC screening/ surveillance uptake that can be detected between arms for different baseline screening/surveillance uptake with 80% power as well as different CRC screen referral rates**

Baseline referral rate for control arm	Sample size (control/ immediate )	Baseline screening/ surveillance uptake for control arm	Estimated difference between arms
60%	100/120	60%	18.0%
65%	100/120	65%	17.2%
70%	120/140	70%	15.0%

**The primary effectiveness outcome for Aim 2 is risk-appropriate CRC screening/surveillance referral for all patients, regardless of risk level.** Outcomes will be compared between arms to determine the impact of decision support on risk-appropriate referrals and screening/surveillance. The risk-appropriate screening/surveillance referral will be determined based on the MeTree algorithm. A binary variable will be created for each patient (1=adherent to risk-appropriate referral, 0=non-adherent to risk-appropriate referral) at 12-month follow up. The appropriateness of the referral will take into account if they were previously (prior to baseline visit) appropriately referred based on the current determination of their risk profile using the MeTree FHH data collection for both arms.

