Data on whether the referral was made will be extracted in a multi-phase process that maximizes efficiency and accuracy. First, we will examine administrative data. FOBT codes are G0328, 82270, 82274, FOBT, FOBT1, FOBT2, FOBT3. We previously found that for 2,836 of 2,989 patients (95%) FOBT use identified by CPT code in the OPC was confirmed in the records of the local VA laboratory performing the test. Similarly, for 2,842 of 2,943 patients (97%) with an FOBT documented in the laboratory records, a CPT code was found in the OPC database. If administrative data reveal a CPT code for colonoscopy or FOBT, then patients will be considered to have undergone that test. If not, then we will examine orders. If no order exists, then we will examine laboratory reports and VISTA imaging. If no evidence of referral or screening is found at this point, then notes will be reviewed to determine whether participants refused, no-showed, received screening outside VA, or there is medical justification (e.g., life-limiting illness) for not receiving screening. The appropriate referral guideline will be based on the risk-categorization of the patient from their FHH. Patients will be coded as risk-appropriate referral or not; recommendation of any option listed as risk-appropriate will be classified as a risk-appropriate referral. Nonadherence to risk-appropriate referral could result from a referral being too aggressive based on risk categorization (e.g., a 40-year old without a FHH of CRC) or that the risk-appropriate referral was not made.

Patient uptake of CRC screening/surveillance recommendation will be evaluated as a secondary outcome. The patient uptake of CRC Screening/Surveillance referral will be examined for the subset of patients that received risk-appropriate referral by having an order in their record following the baseline visit for a CRC screening/surveillance referral. A binary variable will be created for each patient that was referred for CRC screening/surveillance (1=uptake of referred CRC screening, 0=no uptake of referred

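### The primary outcome is scored without checking why a colonoscopy was done, so a diagnostic examination can count as an over-aggressive referral in a younger patient or as a screening referral in an older one

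*Combined protocol and SAP*

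**What the plan says.** All of this stands in the combined protocol and SAP under Analyses for Aims 1-2. The primary effectiveness outcome for Aim 2 is binary: adherent or not to a risk-appropriate screening/surveillance referral at 12 months. The standard comes from the risk tool: "The risk-appropriate screening/surveillance referral will be determined based on the MeTree algorithm". The paragraph on extracting referral data adds: "The appropriate referral guideline will be based on the risk-categorization of the patient from their FHH".

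The same paragraph gives the order of extraction.

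- Administrative data come first: "If administrative data reveal a CPT code for colonoscopy or FOBT, then patients will be considered to have undergone that test".
- Orders, and then laboratory reports and imaging, are examined only when the step before finds nothing.
- Notes come last: "If no evidence of referral or screening is found at this point, then notes will be reviewed". They are read for refusal, no-show, screening outside VA, or whether "there is medical justification (e.g., life-limiting illness) for not receiving screening".

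Scoring works in both directions. On one side, "recommendation of any option listed as risk-appropriate will be classified as a risk-appropriate referral". On the other, "Nonadherence to risk-appropriate referral could result from a referral being too aggressive based on risk categorization", with a 40-year-old without family history as the example.

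No section separates screening or surveillance colonoscopy from diagnostic colonoscopy. The reference list holds two papers on finding colonoscopy indication from administrative data (37 and 42). Reference 42 is cited only at the sentence on fee basis files, and 37 is not cited in the text.

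**The concern.** The outcome is meant to measure a screening decision, which is what decision support can change. A colonoscopy ordered for bleeding or another symptom is not such a decision, yet the extraction rule handles it like any other colonoscopy. The only clinical-reason check excuses a missing test; nothing asks the reason for a test that took place.

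The score then depends on age. In a younger patient without family history, a symptom-driven colonoscopy fits the plan's own example of over-referral and can score 0. In a patient old enough for colonoscopy to be a listed option, it scores 1. At stake are some loss of contrast between the arms and the meaning of the over-referral route to a score of 0, which would mix provider over-referral with symptom work-up.

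**Working it through.** **1. Can both cases occur?** Eligibility is age 40-64. The exclusion of endoscopy covers the 3 years before entry, not the 12 months of follow-up. The documents do not give the age at which the risk tool starts to list colonoscopy for average-risk patients, so below, younger and older mean below and above that unstated age.

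**2. Does a code for a test bear on a referral outcome?** Yes. The code search is the first step of the process introduced as finding whether the referral was made, and the note-review step treats evidence of referral and evidence of screening as alternatives.

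**3. The plan's own figure.** Inputs from the sample size section: 60% v 73%, 240 per arm, 20 providers per arm, ICC 0.02, 5% type I error. Two-sided testing is stated with the analysis methods.

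- Patients per provider: 240/20 = 12.
- Design effect: 1 + (12 - 1) x 0.02 = 1.22.
- Effective size per arm: 240/1.22 = 196.7.
- Power for 60% v 73%: 0.78. The difference detectable with 80% power is 13.2-13.3 points, against 13.2 in Table 1.

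The stated design reproduces and is not in dispute.

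**4. Equal diagnostic rates.** Let q be the share of each arm with a diagnostic colonoscopy in 12 months, unrelated to the score the patient would otherwise have. The documents give no value, so q = 3-6% is an assumption: 500 x 0.03 = 15 to 500 x 0.06 = 30 patients. For a true proportion p:

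- older, score forced to 1: p + (1 - p)q
- younger, score forced to 0: p(1 - q)

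In both groups the arm difference becomes 13 x (1 - q), whatever the age mix.

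- q = 3%: 13 x 0.97 = 12.6 points, a loss of 0.4.
- q = 6%: 13 x 0.94 = 12.2 points, a loss of 0.8.

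With 75% of patients older (also assumed), power is 0.76 at q = 3%, 0.74 at 5% and 0.72 at 8%.

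**5. Only the younger group in error.** If a diagnostic examination in an older patient properly counts as leaving screening not due, only the younger quarter is misclassified:

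- patients: 500 x 0.03 x 0.25 = 3.75 to 500 x 0.06 x 0.25 = 7.5, about 4-8
- loss: 13 x 0.03 x 0.25 = 0.10 to 13 x 0.06 x 0.25 = 0.20 points

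This equals an all-younger sample with q between 0.75% and 1.5%. Power in that setting is 0.77 at 1% and 0.76 at 2%, so it stays at about 0.76 or above.

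**6. Unequal rates.** Suppose no true effect (60% in both arms), 75% older, and q of 6% in the immediate arm against 3% in the control arm (all illustrative). The spurious difference is:

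- both age groups in error: 0.03 x (0.75 x 0.40 - 0.25 x 0.60) = 0.03 x 0.15 = +0.45 points
- only the younger in error: -0.03 x 0.25 x 0.60 = -0.45 points

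Swapping the arms reverses both signs, so the direction cannot be known in advance.

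**The case against.** The strongest reply is that the plan omits a rule rather than states a wrong one. No sentence says that a colonoscopy for bleeding is an over-aggressive referral, and the age threshold sits in an algorithm that the documents do not show. This stands in part: the younger-patient error is what the rule permits if followed literally, not something the plan announces. But the rule is operative, and no other section overrides it.

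A reader might infer that older and younger patients are equally misclassified. The documents do not support that. The plan already takes prior appropriate referral into account, so being up to date is part of the concept, and a diagnostic examination may leave an older patient not due. A reader might also infer that family history is the whole standard; the plan's own example shows that age counts, and prior referral does too.

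Some protection exists. Patients with prior colorectal cancer, inflammatory bowel disease, adenomatous polyps or recent endoscopy are excluded, which removes some of those likeliest to have a diagnostic colonoscopy. The section on personnel training and quality control promises a detailed abstraction protocol and data dictionary, which could hold an indication rule. It is not in the documents, and a rule that defines the primary outcome belongs in the plan.

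Finally, the plan concedes that abstractors cannot be blinded. Asking them to judge indication replaces an objective code with a judgement that could differ by arm. That is a real cost, and it shapes the fix.

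**Conclusion.** The point holds as a modest gap in the definition of the primary outcome. Followed as written, the rule can score a diagnostic colonoscopy as over-referral in a younger patient without family history and credits one as a screening referral in an older patient, the second error being the milder. With equal rates of 3-6% per arm, the 13-point difference loses at most about 0.4-0.8 points, or about 0.1-0.2 points if only a younger quarter is truly misclassified. The rate and the age split are both assumptions.

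A reader might infer that the arm difference is always pulled toward zero. That needs equal diagnostic rates in the two arms, which the documents do not address. Nor do the figures suggest that the sample size fails or that a positive result would be spurious. The case for acting is that the remedy is cheap and that over-referral, one of the two routes to a score of 0, cannot be interpreted without knowing the indication.

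**What to change.** - For each colonoscopy found by code or order, abstract the indication (screening/surveillance, diagnostic, unclear) from the order or procedure note. Use a written rule, identical in both arms and covered by the existing 15% duplicate abstraction.
- Score a diagnostic colonoscopy neither as too aggressive nor as a screening referral. Score the patient on other orders and on whether screening was still due.
- Assign unclear indications to a default fixed in advance.
- Report the all-codes version as a sensitivity analysis.

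The cost is one added field for the subset with a colonoscopy, completed by existing staff from records to which they already have access. Design and sample size do not change. The downside is that some indications will be unclear and that unblinded abstractors will judge them; the fixed rule and the all-codes analysis limit that risk but do not remove it.

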## Protocol: The Impact of Family History and Decision Support on High-Risk Cancer Screening

CRC screening) at 12-month follow up. Data on whether participants completed the CRC screening test will be obtained in a multi-step process. At the time of data abstraction, we will make a determination about whether to examine fee basis files for screens performed by non-VA providers according to whether the Durham and/or Madison VA is outsourcing CRC screening. Patients will be considered adherent if their medical record shows any risk-appropriate CRC test(s) performed in the time between completion of the computer program in clinic and 12-month follow-up.

Referral for genetic consultation will be examined as a secondary outcome. This outcome is risk-appropriate referral for genetic consultation or not. Because the Durham VAMC is online with GMS, a consult option will be generated to refer patients to GMS for genetic consultation, which may or may not include genetic testing. The Madison VAMC is not online with GMS. Therefore, fee basis files will be reviewed to determine if genetic counseling or testing was performed outside VA. The RA will review PCPs' consults and progress notes subsequent to the visit associated with completion of MeTree FHH regarding recommendations for genetic consultation. GI notes will also be reviewed to determine if a consult to GMS was made. Appropriate referral based on risk level will be classified as adherence. We will also examine the rate of receipt of a genetic consultation by conferring with GMS (which may be lower than the referral rate if the patient declines). As a relatively small proportion of participants are expected to receive genetic referral (6.4% in the Cone Health study), we will be underpowered to detect a significant effect. However, the descriptive rates will be informative from a policy perspective.

Process data will be collected to inform eventual implementation. During the study, process data will be collected, including detailed records on enrollment, field notes from the study coordinator regarding the need to assist participants in completing MeTree, modifications to the program or decision support sheets, and any communication with PCPs (comments, questions). Enrollment and completion rates (the number of patients contacted who agree to have a baseline visit and who complete MeTree) will be calculated from information collected in the tracking database. At the end of the study, all enrolled PCPs will complete an exit survey about their experience with the intervention and impact on workflow.

Analyses will compare the risk-appropriate referral rate between patients randomly assigned to the immediate vs. waitlist control arm. A binary variable will be created for each patient (1=adherent to risk-appropriate referral, 0=non-adherent to risk-appropriate referral) at 12-month follow up. Patients with the same PCP may have more similar outcomes as compared to patients with a different PCP. Therefore, we plan to use Generalized Estimating Equations (GEE) as our primary analysis tool. The regression coefficients from a GEE model have essentially the same interpretation as those from a standard regression analysis but are more appropriate because they properly incorporate the within-PCP correlation. When using GEE methods, it is only necessary to specify the general structure of the mean and correlation between repeated observations. Because the outcome is binary, we will use a GEE with a logit link function and an exchangeable correlation structure. In addition, we will use empirical standard errors for inference because they are robust to misspecifications of the correlation structure. The hypothesis for Aim 1 will be tested using the following model of the mean structure:  $\text{logit}(\pi_{ij}) = \beta_0 + \text{ARM} * \beta_1$  where  $\pi_{ij}$  represents probability of risk-appropriate testing adherence for patient  $i$  seen by physician  $j$ . ARM is the dummy-coded intervention arm. A positive, significant estimate for  $\beta_1$  provides evidence that patients who receive the intervention immediately have higher risk-appropriate referrals for CRC screening/surveillance than those in the wait-list control arm. PROC GENMOD in SAS (Cary, NC) will be used to fit the GEE model.

Secondary outcomes for Aim 2 are uptake of referred CRC screening test and risk-appropriate referral for genetic counseling. A binary variable will be created for each patient (1=uptake of referred CRC screening, 0=no uptake of referred CRC screening). Note that determination of uptake will depend on each patient's risk-appropriate referral. For patients for whom multiple tests are appropriate, uptake will be

## Protocol: The Impact of Family History and Decision Support on High-Risk Cancer Screening

defined by performance of any of them. For the referral for genetic consultation outcome, all patients eligible for genetic consultation based on their risk profile from FHH will have their EMR audited to determine whether a risk-appropriate genetic consult referral was documented. A binary variable will be created for each patient (1=presence of risk-appropriate genetic consult referral, 0=absence) at 12-month follow up. A similar variable will be created to indicate whether participants received the recommended genetic consultation. As these secondary outcomes are binary, we will follow the same modeling strategy using GEE as described for the primary outcome. In exploratory analyses, similar outcomes will be created for the other cancer types (breast and ovarian) as described for CRC. We will calculate descriptive statistics for these outcomes and, if sample size is adequate, we will fit similar GEE as described for CRC.

The primary analyses for this cluster-randomized trial will be conducted on an intent-to-treat basis; participants will be analyzed in the group to which they were randomized, regardless of intervention adherence. Additional supporting analyses focusing on alternative, more restrictive analytic cohorts (e.g., per-protocol analysis) may be considered as exploratory analyses to provide additional information about the impact of amount of exposure to the intervention. Given that the outcomes will be determined based on EMR review over a 12-month period, there should be very little missing data. The most likely scenarios are that a participant dies during the study or leaves the VA system before completion of the 12-month follow-up period. However, we do not expect this to occur at a high rate; as needed, we will explore the impact with sensitivity analyses.

The main conclusions drawn from this trial will be based on the pre-specified primary and secondary hypotheses outlined previously and will be tested with two-sided p-values at the standard 0.05 level. For both primary and secondary outcomes, stratification variables (provider type and patient age categorization) will be included in GEE models. Statistical analyses will be performed using SAS for Windows (Version 9.2: SAS Institute, Cary, NC) and R (<http://www.R-project.org>).

### Aim 3

**The evaluation of Aim 3 employs a single, holistic case study design with the participating Durham and Madison VA primary clinics as the unit of analysis.** Although GMM will be used in 3 different clinics, our focus is to examine the holistic nature of GMM implementation. Should we find clinic-level variation in identification, referral, or screening/surveillance rates (Aims 1-2), we will use a replicated case study design to describe implementation experiences for each clinic. Case study design is well-suited for describing the implementation of GMM in the VA system, which has not been examined before. In addition to permitting in-depth analysis of individual cases, case study methods offer strategies for systematic contextual analysis from multiple sources of information.

To ensure that implementation evaluation in this case study includes all the relevant evidence and includes rival or conflicting interpretations, we will employ a mixed methods approach, collecting information about GMM implementation from multiple sources of data. Quantitative data will come from EMR and administrative data collected in Aims 1-2. Qualitative data will be collected via semi-structured interviews with clinic staff and administrators in Aim 3, conducting at the conclusion of Aims 1 and 2. These interviews will provide rich contextual data regarding clinic structure and operations that are otherwise unobservable in secondary data.

Potential participants will include PCPs and clinic leaders (nurse manager, charge nurse, and clinic director) from each site, the Chief of Ambulatory Care, and the Chief of Medicine. A recruitment letter will be emailed; this letter will note that leaders/PCPs may opt out by contacting one of the study team members. If we do not hear from them, then we will follow up by telephone. Purposeful sampling in

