**Aim 1:** Determine whether FHH collection via MeTree improves identification of patients at higher familial risk for CRC by comparing rates of high-risk identification in the medical record prior to study enrollment to rates of high-risk identification following MeTree completion.

**Aim 2:** Evaluate whether providing decision support to patients and PCPs improves risk-appropriate PCP referrals for, and patient uptake of, CRC screening/surveillance.

The secondary aims are:

**Aim 3:** Assess experience with decision support and effects on workflow from PCPs, and obtain information to inform eventual implementation in the VA healthcare system from administrative leaders, via qualitative interviews.

**Aim 4:** Conduct cost-consequence and budget-impact analyses of implementing FHH collection and GMM decision support in VA.

If MeTree effectively increases identification of high-risk Veterans, and decision support effectively increases appropriate CRC screening for high-risk Veterans, then we will be poised to inform and evaluate implementation of GMM in VA on a larger scale and for a larger disease set.

## Methods for Aims 1 and 2

**Sample selection and enrollment.** We will enroll primary care providers (PCPs) and patients from the Madison VAMC, Durham VAMC, Raleigh, Hillandale, and Greenville clinics. To achieve our target sample size of 500 patients who complete MeTree, we will enroll all eligible providers. We anticipate enrolling 40 providers, with 12-13 patients per provider; however, the number of patients enrolled per provider may vary if fewer providers enroll. PCP and patient eligibility will be determined from the following study inclusion/exclusion criteria.

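### The GEE models omit site although about 40 PCPs are randomized across Madison and the Durham-area clinics: a possible loss of precision that is cheap to avoid

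*Combined protocol and SAP*

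**What the plan says.** All references are to the combined protocol and SAP.

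- **Model.** Under Analyses for Aims 1-2, the displayed mean model has an intercept and one term: "ARM is the dummy-coded intervention arm". For the binary outcome, "we will use a GEE with a logit link function and an exchangeable correlation structure", with PCP as the cluster and empirical standard errors. The closing analysis paragraph adds that "stratification variables (provider type and patient age categorization) will be included in GEE models". Neither place mentions site or clinic.
- **Sites and clusters.** Sample selection and enrollment states: "We will enroll primary care providers (PCPs) and patients from the Madison VAMC, Durham VAMC, Raleigh, Hillandale, and Greenville clinics". It also states: "We anticipate enrolling 40 providers, with 12-13 patients per provider". The power section fixes 20 PCPs per arm.
- **Randomization.** PCPs are randomized after consent. The paragraph describing this names no strata.
- **Stated site differences.** For genetic consultation, Durham has a consult option and "The Madison VAMC is not online with GMS", so fee basis files are searched for Madison. For CRC uptake, use of fee basis files is decided at abstraction, "according to whether the Durham and/or Madison VA is outsourcing CRC screening". Both outcomes are secondary.
- **Primary outcome.** Referral is extracted by one multi-phase sequence with no site-specific step.
- **Foreseen variation.** The Aim 3 section allows for clinic-level variation in identification, referral and screening rates, but uses it only to choose the case-study design.

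**The concern.** Site is known for every PCP before randomization and could predict referral. With about 20 PCPs per arm and no described balancing by site, the arms can differ by chance in their share of Madison PCPs. In a model without site, any site difference in referral is then part of the between-PCP variance and widens the uncertainty of the arm effect. Planned power is only about 79-80%, so there is little slack. One pre-specified indicator would remove that component at small cost.

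**Working it through.** **1. The plan's own figure.** Inputs from Sample Size and Power Considerations and Table 1: control rate 60%, difference 13 points (13.2 in Table 1), two-sided 5%, 80% power, ICC 0.02, 240 patients per arm over 20 PCPs, so 12 per PCP.

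- Design effect = 1 + (12 - 1) × 0.02 = 1.22.
- At 13.2 points: unpooled 197 × 1.22 = 240 per arm; pooled 200 × 1.22 = 244. The plan's 240 is reproduced.
- Loss to follow-up: 480 / 0.96 = 500.
- SE at 13 points = sqrt((0.60 × 0.40 + 0.73 × 0.27) × 1.22 / 240) = 4.71 points.
- Power = Phi(13 / 4.71 - 1.96) = about 79%.

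**2. Chance imbalance in site.** The documents do not give the site split, so I assume that M of the 40 PCPs are at one site, with M from 8 to 20. Under a 20/20 split the between-arm difference in site share has SD = (2/20) × sqrt(20 × (M/40) × (1 - M/40) × 20/39).

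- M = 8: SD 12.8 points; chance of a difference of at least 20 points is 24%.
- M = 20: SD 16.0 points; chance 34%.

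**3. Effect on power if site variance is additional to the ICC.** The site gap D in referral is also assumed, since none is stated. The shift in the arm contrast has SD = D × (SD of share difference). Power = Phi(13 / sqrt(4.71² + shift SD²) - 1.96). The site contribution to the ICC is (M/40)(1 - M/40)D² / 0.24. Ranges run from M = 8 to M = 20.

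| Assumed gap D | Shift SD (points) | Site part of ICC | Power without site |
|---|---|---|---|
| 0 | 0 | 0 | 79% |
| 5 points | 0.6-0.8 | 0.002-0.003 | 78% |
| 10 points | 1.3-1.6 | 0.007-0.010 | 74-76% |
| 15 points | 1.9-2.4 | 0.015-0.023 | 69-72% |
| 20 points | 2.6-3.2 | 0.027-0.042 | 63-68% |

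**4. If the ICC of 0.02 already includes site variance.** Unadjusted power stays at 79%, so nothing is lost against plan. Adjustment then subtracts the site component. At a 10-point gap, sqrt(4.714² - 1.281²) = 4.537 points (M = 8) and sqrt(4.714² - 1.601²) = 4.434 points (M = 20), giving power of about 82% and 83%. A 20-point gap (0.027 or more) does not fit inside 0.02, so some loss against plan would follow.

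**5. Simulated GEE.** Exchangeable, uncorrected robust SE, 40 clusters of 12, within-site ICC 0.02, unstratified randomization.

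| Split, gap, runs per scenario | Power without / with site | Type I error without / with site |
|---|---|---|
| 14/26, none, 1000 | 80% / 80% | 7.5% / 8.3% |
| 14/26, 10 points, 1000 | 75% / 78% | 6.9% / 7.4% |
| 20/20, 10 points, 2000 | 74% / 78% | 5.8% / 6.7% |
| 20/20, 20 points, 2000 | 65% / 82% | 5.0% / 6.0% |

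Omitting site does not raise type I error: the no-gap row, where site is irrelevant, already exceeds 5%. That excess reflects uncorrected sandwich errors with 40 clusters. It is up to 1 point larger with the site term, so a small part of the simulated power gain comes from a slightly liberal test.

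**The case against.** A reader might infer that, because the plan describes different pathways and data sources at Durham and Madison, the primary comparison is distorted. The documents do not support that. The one difference stated as fact concerns genetic consultation. The outsourcing clause for uptake is a condition to be checked, not a statement that the sites differ. Primary referral data come from a single sequence whose last step reviews notes for, among other things, screening received outside VA. Staff at either site may abstract, under a common protocol with 15% independent re-abstraction. This part of the objection stands.

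A reader might also take a fall in power to the mid-60s as the expected cost. That needs a gap of about 20 points stacked on the planned ICC. The plan calls 0.02 conservative and cites a median of 0.01 (IQR 0 to 0.03); a 20-point gap alone would contribute 0.027-0.042. At 5 points the cost is about 1 power point. This also stands.

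Finally, randomization makes the expected imbalance zero, and PCP-clustered standard errors allow for it. If randomization was in fact stratified by site, leaving site out gives over-wide intervals, which is conservative. That removes any claim of bias. It does not remove the case for adjustment: in the simulation with no site gap the term left power unchanged, and with a gap it recovers precision whether or not randomization was stratified.

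**Conclusion.** The point holds as one of precision. Site is absent from the models and from the named stratification variables, about 40 PCPs are randomized across two VA systems, and the plan itself allows for variation in referral between clinics. The effect on the primary outcome cannot be sized from the documents, because they give neither the site split nor a site gap. Under the stated assumptions the loss is about 1 power point at a 5-point gap, 3 to 5 points at 10, and 11 to 16 points at 20. It is smaller or nil against plan if 0.02 already covers site. There is no ground for claiming systematic bias or type I inflation from the omission. The documented site differences bear on genetic consultation and, conditionally, on CRC uptake.

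**What to change.** - Pre-specify a two-level site indicator (Durham-area clinics versus Madison) in the primary GEE and the CRC-uptake GEE, alongside provider type and age category.
- Use small-sample-corrected empirical standard errors (for example Mancl-DeRouen or Kauermann-Carroll), because there are only about 40 clusters. The simulation supports this with or without the site term.
- Report genetic referral descriptively by site. At the plan's expected 6.4%, 500 patients yield about 32 referrals (0.064 × 500), and the plan already calls this outcome underpowered.
- State whether PCP randomization was stratified by site.
- If outcomes have already been analysed, present the site-adjusted model as a labelled sensitivity analysis.

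Cost: one of about 38 between-cluster degrees of freedom and a little more analysis work. Site is known for every PCP, so no new data are needed.
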